- Proportion of patients with clinical symptom requiring hospitalization, oxygen therapy, or experiencing mortality due to SARS-CoV-2 infection up to Day 28 in all randomized patients.
- Time to clinical recovery up to Day 14 in high-risk patients.
- Time to clinical recovery up to Day 14 in all randomized patients.

The key secondary endpoints will be tested at the 2-sided significance level of 5% on the ITT set (for high-risk patients, ITT set - High Risk) using the p-value from stratified CMH test for binary endpoints or stratified log-rank test for time to event endpoints.

The first key secondary endpoint will be tested only if the primary endpoint is statistically significant, and the next key secondary endpoint will be tested only if the previous key secondary endpoint is statistically significant. The supportive analysis will be performed on ITTI set (for high-risk patients, ITTI set - High Risk).

Binary endpoints will be summarized using frequency table, and difference of proportions between treatment groups and corresponding 95% stratified Newcombe CI with CMH weights will be presented along with p-value from stratified CMH test.

For time to event endpoints, Kaplan-Meier methodology will be used to estimate the 25th percentile, 50th percentile (median) and 75th percentile in each treatment arm. The Brookmeyer-Crowley methodology will be used to construct the 95% CI for each percentile. The treatment difference will be assessed by the stratified log-rank test presenting p-value. The rate ratio and its 95% CI from the stratified Cox proportional hazard model will be presented.

For time to clinical recovery endpoints, patients who report at least one symptom at baseline will be included in the analysis.

7.8.3.3 Secondary Efficacy Analysis for both Part 1 and Part 2

The secondary efficacy endpoints will be assessed up to Day 14 and up to Day 28 and analyzed on both ITTI and ITT sets.

For Part 1, time to event analyses will be analyzed using Kaplan-Meier analysis. The others will be summarized using descriptive statistics or frequency tables.

For Part 2, CI and p-value will be presented for comparison between treatment groups in a descriptive manner. Therefore, no adjustments for multiple testing will be made. Statistical analysis method to calculate CI and p-value are described below.

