Binary endpoints will be summarized using frequency table, and difference of proportions between treatment groups and corresponding 95% stratified Newcombe CI with CMH weights will be presented along with p-value from stratified CMH test.

For time to event endpoints, Kaplan-Meier methodology will be used to estimate the 25th percentile, 50th percentile (median) and 75th percentile in each treatment arm. The Brookmeyer-Crowley methodology will be used to construct the 95% CI for each percentile. The treatment difference will be assessed by the stratified log-rank test presenting p-value. The rate ratio and its 95% CI from the stratified Cox proportional hazard model will be presented.

For time to clinical recovery endpoints, patients who report at least one symptom at baseline will be included in the analysis.

Continuous endpoints will be summarized using descriptive statistics and analyzed using analysis of covariance presenting a point estimate, p-value and 95% CI for the treatment

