7.8.3.3.2 Intensive Care Unit Transfer

The proportion of patients transferring to intensive care unit due to SARS-CoV-2 infection will be separately summarized by each treatment group.

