7.8.3.3.10 Other Known SARS-CoV-2 Infection Symptoms

Scores recorded for each of the symptoms in the SARS-CoV-2 Infection Symptom Checklist 2 at each visit will be summarized by each treatment group using descriptive statistics.

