group. For the comparison between treatment groups, the primary efficacy endpoint will be tested at the 2-sided significance level of 5% on the ITT set – High Risk using Cochran-Mantel-Haenszel (CMH) test stratified by age (≥ 60 years vs. < 60 years), baseline comorbidities (Yes vs. No) and region (United States vs. European Union vs. other). For the region, the patients in Asia are included in other category as the number of patients in Asia was confirmed to be around 1% during blinded DRM. The difference of proportions between two treatment groups estimated using CMH weights will also be provided along with the 95% stratified Newcombe CI with CMH weights. Supportive analysis will be performed on ITTI set – High Risk using the same analysis method for the primary efficacy analysis. For sensitivity analysis, Fisher's exact test will be conducted on ITT set – High Risk. The 95% exact CI (Chan and Zhang 1999) for the treatment difference will also be provided. Additionally, sensitivity analysis will be performed for the primary analysis excluding 7 patients randomized in site 6179 which terminated its participation in the study by Institutional Review Board (IRB)'s decision due to serious and continuing non-compliance to the protocol and GCP.

In addition, the analysis for the following subgroups will be conducted on ITT set – High Risk:

- Age (< 60 years, ≥ 60 years, ≥ 50 years)
- Baseline comorbidities (Yes, No)
- Region (United States, Asia, European Union, Other)
- Race (White, Black or African American, American Indian or Alaska Native, Asian, Native Hawaiian or Other Pacific Islander, Not Allowed by Investigator Country Regulations, Other)
- Sex (Male, Female)

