- Time to negative conversion in nasopharyngeal swab specimen based on RT-qPCR (after study drug administration)
 - Time to negative conversion in nasopharyngeal swab specimen based on RT-qPCR will be calculated as (Date/time of event or censoring – Date/time of study drug administration)
- Time to National Early Warning Score 2 (NEWS2) of 0 (after study drug administration)
 - Patients whose sum of each parameter score meet 0 will be considered as satisfying NEWS2 of 0.
 - Time to NEWS2 of 0 will be calculated as (Date of event or censoring – Date of study drug administration).
- Scores of other known SARS-CoV-2 Infection symptoms such as vomiting, diarrhea, loss of taste or smell at each visit

The secondary efficacy endpoints listed in this section will be analyzed on both ITT and ITTI sets. Confidence interval and p-value will be presented for comparison between treatment groups in a descriptive manner with no adjustments for multiple testing.

Binary endpoints and time to event endpoints will be summarized and analyzed using the same statistical method as the key secondary endpoints ([Section 9.2](#)). For time to event endpoint, time to event will be defined as the elapsed time (in days) from the study drug administration to the earliest day satisfying condition for event. The same censoring rules used for clinical recovery of the key secondary endpoints ([Section 9.2](#)) will be applied.

Continuous endpoints will be summarized using descriptive statistics and analyzed using Analysis of Covariance (ANCOVA) presenting a point estimate, p-value and 95% CI for the treatment difference. Covariates for ANCOVA will include stratification factors used for the primary analysis.

For analysis of time to event endpoints, the following patients will be included in the analysis set:

- Time to clinical recovery: Patients who report at least one symptom at baseline
- Time to negative conversion: Patients who have positive result confirmed based on the negative threshold (as defined in [Section 11.1.1](#)) in the analysis at baseline (or Day 2/Day 3). The same analysis set will be used for the proportion of negative conversion.
- Time to NEWS2 of 0: Patients who have NEWS2 > 0 at baseline

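### The Checklist 2 ANCOVA in SAP 9.3 does not name the item's own baseline score as a covariate; leaving it out may widen the confidence intervals needlessly

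*SAP*

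**What the plan says.** SAP 9.3 lists as a secondary efficacy endpoint: "Scores of other known SARS-CoV-2 Infection symptoms such as vomiting, diarrhea, loss of taste or smell at each visit". For the endpoints of that section it states: "Confidence interval and p-value will be presented for comparison between treatment groups in a descriptive manner with no adjustments for multiple testing". It gives methods for three kinds of endpoint: binary, time-to-event and continuous. Continuous endpoints go to ANCOVA, and the only statement on covariates is: "Covariates for ANCOVA will include stratification factors used for the primary analysis". SAP 9.1 gives those factors as age (cut at 60), baseline comorbidity (yes or no) and region in three levels.

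Protocol 7.8.3.3 agrees on method. It says "For Part 2, CI and p-value will be presented for comparison between treatment groups in a descriptive manner", and that continuous endpoints are "analyzed using analysis of covariance presenting a point estimate, p-value and 95% CI". It names no covariates.

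Protocol 7.8.3.3.10, the paragraph specific to Checklist 2, says only that the scores "at each visit will be summarized by each treatment group using descriptive statistics".

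The baseline information exists. SAP 9.4.2 has Checklist 2 recorded at Screening and again on Day 1 before dosing. SAP 5.5 defines baseline as the last available value before study drug. SAP 9.4.2 gives no analysis model for the checklist, and SAP Section 12 (changes in the planned analysis) does not address the point.

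**The concern.** All three named covariates are categorical design factors. For a symptom score measured repeatedly, the same item's score before dosing is the obvious candidate predictor of the later score, and the trial already collects it. A model without it is valid, but it leaves in the residual any variation that the baseline score could explain.

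What is at stake is precision, and a model choice that should be settled before unblinding. The covariate sentence can be read as a complete list or as a minimum, so two analysts could fit different models to the same data. The choice recurs for four items, at each visit and in two analysis sets (ITT and ITTI). Bias is not at issue, and neither is the type I error of the confirmatory tests, because these p-values are outside the fixed sequence.

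Duration of fever, also handled as a continuous endpoint, has no pre-dose value of the same variable. Stratification factors alone are coherent there.

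**Working it through.** **Does ANCOVA apply to Checklist 2?** No sentence says so outright. The scores run 0–3 (vomiting, diarrhea) and 0–2 (smell, taste), so they are neither binary nor time-to-event. SAP 9.3 promises inference for its listed endpoints and leaves only ANCOVA. The descriptive wording in Protocol 7.8.3.3.10 does not settle the matter. Protocol 7.8.3.3.2 likewise says only that ICU transfer "will be separately summarized by each treatment group", yet Protocol 7.8.3.3 gives every Part 2 binary secondary endpoint a CMH p-value.

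**Inputs.** 650 patients per arm (SAP 4.1 and 5.2). The correlation r between baseline and post-dose score within strata is not in the documents and is assumed. They also give no SD, interval width or power for these scores, so there is no stated figure to reproduce.

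**Step 1: formula.** In units of the within-stratum SD:

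- Half-width without the baseline score: 1.96 × √(2/650) = 0.1087.
- Half-width with it: 0.1087 × √(1−r²).
- Excess width if omitted: 1/√(1−r²) − 1. This does not depend on arm size, so it applies equally to the ITTI set.
- Equivalent extra patients per arm: 650 × (1/(1−r²) − 1).

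| r (assumed) | Half-width with baseline (SD) | Excess if omitted | Equivalent extra patients per arm |
|---|---|---|---|
| 0.1 | 0.1082 | 0.5% | 6.6 |
| 0.3 | 0.1037 | 4.8% | 64.3 |
| 0.5 | 0.0942 | 15.5% | 216.7 |

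Chance baseline imbalance is part of this loss and does not add to it.

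**Step 2: floor effect.** Many patients may score 0. The symptom list in inclusion criterion 6 (Protocol 4.1.1) contains none of the Checklist 2 symptoms, so a patient can qualify with all four items at zero. Scores bunched at 0 lower the observable correlation. Pairs of correlated normal variables were cut into ordered scores at assumed frequencies:

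| Item (assumed) | Latent correlation | Observed r | Excess |
|---|---|---|---|
| Rare, 0–3: 5% above 0 at baseline, 3% post-dose | 0.3 | 0.089 | 0.4% |
| Same | 0.5 | 0.206 | 2.2% |
| Common, 0–2: 40% above 0 at baseline, 25% post-dose | 0.3 | 0.202 | 2.1% |
| Same | 0.5 | 0.354 | 6.9% |

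A separate simulation of 1,300-patient trials, with somewhat different cut-points, agrees. At latent 0.3 and 0.5 the excess is 1.9% and 6.3% for a 0–2 item, and 0.6% and 2.8% for a sparse 0–3 item. At latent 0.7 the 0–2 item reaches an observed r of 0.51 and an excess of 16.2%; the sparse item reaches 0.41 and 10.1%. At zero correlation nothing is lost.

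**Step 3: the proposed model.** Two thousand simulated trials per scenario were run with 650 per arm, no treatment effect and the stratification factors in both models. An assumed 5% of patients lacked a baseline score and were handled by the pooled mean plus a missing indicator. Mean half-widths in score points, without and with baseline, were:

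- Common item: 0.0712 and 0.0698 at latent 0.3 (1.9%); 0.0712 and 0.0668 at latent 0.5 (6.5%).
- Rare item: 0.0270 and 0.0269 at latent 0.3 (0.4%); 0.0271 and 0.0264 at latent 0.5 (2.4%).

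Percentages are from unrounded widths. Coverage of the adjusted 95% interval was 94.8% to 95.0%.

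**The case against.** The strongest reply is that no error has been shown. The covariate sentence does not claim to be complete, the model as written is valid, and adding a prognostic covariate is an efficiency preference. That the plan is valid stands, and it is why the point is rated low. But the sentence leaves the model undetermined, and the better version needs no new data.

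A second reply is that ANCOVA for Checklist 2 is an inference. The items are ordered categories, the comparable Checklist 1 gets a shift table, and the checklist's own protocol paragraph mentions only descriptive statistics. If the ANCOVA sentence was meant for duration of fever alone, the covariates are adequate. This stands in part, because the intended method is not stated. But SAP 9.3 promises a confidence interval and p-value for the endpoints it lists, so the text needs clarifying either way.

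A third reply is that the larger figures are not realistic. In the Step 2 table the highest observed r is 0.354, equivalent to 650 × (1/(1−0.354²) − 1) ≈ 93 patients per arm, well short of 217. The largest reduction in half-width in Step 3 is 0.0712 − 0.0668 = 0.0044 points on a 0–2 scale, which is unlikely to change how a descriptive result is read. This is largely fair. An r near 0.5 appeared only for the three-level item, at a latent correlation of 0.7. The 15% figure should be read as the top of an assumed range.

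**Conclusion.** The concern holds as a minor precision point. SAP 9.3 does not name the item's baseline score as a covariate. If it is left out, the Checklist 2 intervals are wider than the collected data require whenever the baseline score predicts the later one.

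The likely cost is small: roughly 0.4% to 2% for rare items and 2% to 7% for common three-level items at latent correlations of 0.3 to 0.5. It reaches about 15% only if the observed within-stratum correlation is near 0.5. All of these rest on assumed correlations and score frequencies, since the documents give neither. They also rest on reading Checklist 2 as falling under the ANCOVA by elimination. Validity and the confirmatory analyses are not affected.

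**What to change.** In SAP 9.3, replace the covariate sentence with:

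*Checklist 2 scores at each visit will be compared by ANCOVA including the baseline score of that item (Section 5.5) and the stratification factors used for the primary analysis; for duration of fever the covariates will be the stratification factors only.*

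Add one sentence with a simple rule that keeps patients without a pre-dose score in the model, for example:

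*A missing baseline score will be replaced by the pooled mean of both arms, with an indicator for missing baseline in the model.*

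Other simple rules would serve; few patients should need one, since baseline can come from either of two pre-dose recordings. If no inference was intended for Checklist 2, SAP 9.3 should say so instead.

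The cost is two sentences, settled before unblinding. No new data are needed, and no protocol change, because Protocol 7.8.3.3 already provides for ANCOVA. Naming the model in SAP 9.3 also makes clear how it relates to the descriptive wording of Protocol 7.8.3.3.10.

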9.4. Patient Diary

Patient diary consists of SARS-CoV-2 Infection Symptom Checklist 1 and 2. Patient diary will be issued to all patients at Screening and patients will be required to record the diary daily from Day 1 until Day 28, and after Day 28 if applicable (Protocol Section 6.1.1.1 and 6.1.1.2) after patients got instructed on how to appropriately complete the patient diary. Signs and symptoms of SARS-CoV-2 infection recorded in the patient diary throughout the study will not be reported as AEs.

9.4.1. SARS-CoV-2 Infection Symptom Checklist 1

SARS-CoV-2 Infection Symptom Checklist 1 consists of 7 symptoms and the intensity of patient's self-aware for each SARS-CoV-2 infection symptom. The 7 symptoms of SARS-CoV-2 infection are feeling feverish, cough, shortness of breath or difficulty breathing, sore throat, body pain or muscle pain, fatigue, and headache. Scores for SARS-CoV-2 infection symptom are absent (0), mild (1), moderate (2), and severe (3), defined as below [Table 2](#):

Table 2. SARS-CoV-2 Infection Symptom Checklist 1

	Intensity (score)	Absent (0)	Mild (1)	Moderate (2)	Severe (3)
1	Symptoms				
	Feeling feverish*				

2	Cough				
3	Shortness of breath or difficulty breathing				
4	Sore throat				
5	Body pain or muscle pain				
6	Fatigue				
7	Headache				

* If patient checks ‘Feeling feverish’ as Mild, Moderate, or Severe, body temperature will be recorded in the patient diary.

Mild: no interference with normal daily activity

Moderate: interferes with normal daily activity

Severe: prevents normal daily activity

The SARS-CoV-2 Infection Symptom Checklist 1 will be recorded once at Screening.

On the date of study drug administration (Day 1), the checklist will be recorded once; before the study drug administration. If Screening visit date and the date of study drug administration are the same, the checklist will be also recorded once; before the study drug administration. From Day 2 and up to Day 28, the checklist will be recorded once a day at approximately 24-hour intervals in the evening (between 6 and 10 PM, approximately).

After Day 28, additional recording of the checklist will be required if following conditions are met:

- For patient who achieves the clinical recovery on Day 28 (or Day 27), the patient will record the checklist until Day 30 (or Day 29) to confirm whether the patient’s condition is maintained at least 48 hours.
- For patient who shows deterioration (at the discretion of the investigator) or is still not recovered, the patient will record the checklist until the achievement of clinical recovery.
- For patient with suspicious ADE occurrence, the patient will record the whole patient diary for 7 days from the day of suspicious ADE occurrence. If suspicious ADE has not resolved or has worsened during the 7 days, same procedure of recording the whole patient diary for 7 days will be repeated from the beginning until the symptoms are resolved and/or no SARS-CoV-2 infection is confirmed by RT-PCR (local).

Body temperature will be collected in the SARS-CoV-2 Infection Symptom Checklist 1 for the patients who record feeling feverish as the baseline symptoms of SARS-CoV-2 infection at Screening, or for the patients who record feeling feverish at any time throughout the study.

The body temperature will be self-measured by the patients, once a day (at approximately 24-hour interval; in the evening [between 6 and 10 PM, approximately]) from the first day on which the patient records feeling feverish until the day of subsidence of a fever (subsides to ≤ 38.0 °C), except Screening visit.

SARS-CoV-2 Infection Symptom Checklist 1 will be summarized by treatment group and visit for the both ITTI and ITT sets, in the form of a shift table to detect changes from baseline.

9.4.2. SARS-CoV-2 Infection Symptom Checklist 2

SARS-CoV-2 Infection Symptom Checklist 2 consists of 4 symptoms and the frequency or intensity of patient’s self-aware for each SARS-CoV-2 infection symptom. The 4 symptoms of SARS-CoV-2 infection included are vomit, diarrhea, sense of smell, and sense of taste. Frequency of vomit or diarrhea in the last 24 hours and intensity of the sense of smell or taste in the last 24 hours will be recorded, defined as below [Table 3](#):

Table 3. SARS-CoV-2 Infection Symptom Checklist 2

No.	Items	Score
1	How many times did you vomit (throw up) in the last 24 hours?	
	I did not vomit at all	0
	1-2 times	1
	3-4 times	2
	5 or more times	3
2	How many times did you have diarrhea (loose or watery stools) in the last 24 hours?	
	I did not have diarrhea at all	0
	1-2 times	1
	3-4 times	2
	5 or more times	3
3	Rate your sense of smell in the last 24 hours.	
	My sense of smell is THE SAME AS usual	0
	My sense of smell is LESS THAN usual	1
	I have NO sense of smell	2
4	Rate your sense of taste in the last 24 hours.	
	My sense of taste is THE SAME AS usual	0
	My sense of taste is LESS THAN usual	1
	I have NO sense of taste	2

The SARS-CoV-2 Infection Symptom Checklist 2 will be recorded once at Screening. On the date of study drug administration (Day 1), the checklist will be recorded once before the study drug administration. If Screening visit date and the date of study drug administration are the same, the checklist will be also recorded once before the study drug administration. From Day 2 and up to Day 28, the checklist will be recorded once a day at approximately 24-hour interval in the evening (between 6 and 10 PM, approximately).

After Day 28, additional recording of the checklist will be required if following conditions are met:

- For patient with suspicious ADE occurrence, the patient will record the whole patient diary for 7 days from the day of suspicious ADE occurrence. If suspicious ADE has not resolved or has worsened during the 7 days, same procedure of

recording the whole patient diary for 7 days will be repeated from the beginning until the symptoms are resolved and/or no SARS-CoV-2 infection is confirmed by RT-PCR (local).

9.5. Disease Status Monitoring

Disease status including requirement of supplemental oxygen, intensive care unit transfer, mechanical ventilation use, hospitalization, and rescue therapy due to SARS-CoV-2 infection will be monitored during the study period (from signing of ICF to EOT).

9.6. NEWS2

NEWS2 physiological parameter including respiratory rate (breaths per minute), SpO₂ Scale 1 (%), SpO₂ Scale 2 (%), Room air or oxygen, Systolic blood pressure (mmHg), Heart rate (beats per minute), Consciousness, Body temperature (°C) will be assessed at time points specified in the schedule of assessment in [Appendix 1](#).

NEWS2 will be calculated by sum of each parameter score in [Appendix 4](#). If there is missing score in some parameter, then NEWS2 will not be calculated. NEWS2 will be summarized by treatment group at each scheduled visit for both ITTI and ITT sets, displaying descriptive statistics.

10. SAFETY ANALYSIS

All safety analyses will be performed in the Safety Set by each treatment group, and all safety listing will be presented for the ITT Set unless otherwise stated.

10.1. Adverse Events

An adverse event (AE) is defined as any untoward medical occurrence in any patient during the study which does not necessarily have to have a causal relationship with the study drug. AEs will be collected from the date of the patient signs on the ICF until the end of the patient's participation in the study. All AEs will be coded to SOC and PT using the MedDRA version 23.1 or higher, and will be graded for intensity according to the National Cancer Institute Common Terminology Criteria for Adverse Events (CTCAE) version 5.0. A treatment-emergent adverse event (TEAE) includes any untoward medical occurrence in a patient after administration of a study drug, which does not necessarily have to have a causal relationship with the study drug. This includes any occurrence that is new or aggravated in severity or frequency from the baseline condition. A TEAE can therefore be any unfavorable and unintended sign (including an abnormal laboratory finding), symptom, or disease temporally associated with the use of the product, whether or not related to the study drug.

For the purpose of inclusion in TEAE tables and categorization of treatment period or Follow-Up period, incomplete AE start and stop dates will be imputed as follows:

If the stop date of an AE is partial or missing, the following rules will be applied.

- Missing day (e.g. XXAUG2020): Assume the last day of the month. (e.g. 31AUG2020)
- Missing day and month (e.g. XXXXX2020): Assume December 31st. (e.g. 31DEC2020)
- Missing day, month and year (e.g. XXXXXXXXXX): Leave it as Missing.

If the start date of an AE is partial or missing the following rules will be applied. If the stop date of the AE is partial, imputed stop date will be used instead of reported stop date.

- If the day of an Adverse Event is missing (e.g. XXAUG2020), the month and year of the partial date will be compared to the date of the first exposure to study drug.
 - If the month and year are equal for both dates, the AE start date will be imputed as the earlier date of: (i) the date of the first exposure to study drug, and (ii) the stop date of the AE.
 - If the month and year are not equal, the AE start date will be imputed as the first day of the month (e.g. 01AUG2020).
- If the day and month is missing (e.g. XXXXX2020), the year of the partial date will be compared to the date of the first exposure to study drug.
 - If the years of both dates are equal, start date will be imputed as the earlier date of: (i) the date of the first exposure to study drug, and (ii) the stop date of the AE.
 - If the year is not equal, start date will be imputed as the 1st of January of the partial date year (e.g. 01JAN2020).
- If the AE start date is missing (e.g. XXXXXXXXXX), start date will be imputed as the earlier date of: (i) the date of the first exposure to study drug, and (ii) the stop date of the AE.

In summaries, AEs will be considered to be related if relationship is possible, probable or definite. AEs with no relationship or intensity will be summarized separately under a missing category.

All AEs will be listed including the following information: Safety Set flag, SOC, PT and Verbatim term; start and stop date/time; TEAE flag; intensity (CTCAE Grade 1 to 5); outcome (Recovered/Resolved, Recovering/Resolving, Recovered/Resolved with Sequelae, Not recovered/Not Resolved, Fatal, Unknown); type of sequelae (If Recovered/Resolved with Sequelae); relationship with study drug (Unrelated, Possible, Probable, Definite); action taken with study drug (Dose not changed, Drug interrupted, Drug withdrawn); any treatment received (No, Medication, Non-Medication Treatment: Specify, Both Medication and Non-Medication Treatment: Specify the Non-Medication Treatment); whether the event was serious (Yes, No); whether the AE classified as infusion related reaction (IRR); period flag (Treatment Period, Follow-Up Period).

